- **(c) Tailored Health Content.** The clinical conditions addressed by Gabby are categorized into 12 health content areas of preconception care as defined in the CDC report. The system is designed to facilitate a user's in-depth exploration of risks pertaining to her. Discussion is directed by the woman based upon her interests and motivations. Gabby allows for sophisticated levels of tailoring. Dialogue generated is specific to the responses of each woman at each turn of dialogue based on the risks identified. The content is further tailored based on the woman's interested in pregnancy prevention versus interested in becoming pregnant.
- **(d) Motivational Interviewing.** The dialogue content of Gabby is adapted to the woman's readiness for change with regard to a specific risk. The intervention follows behavioral construct tailoring theory, which builds on Prochaska and DiClemente's Transtheoretical Model that behavior change is a process, not an event, and that people move through five stages¹⁵ that are *pre-contemplation, contemplation, preparation, action, and maintenance*. For example, those women who are pre-contemplative for a specific risk will receive motivational interviewing dialogue to try to move them to contemplation. Ongoing interactions help the user resolve ambivalence and use problem-solving approaches to support participants with a risk-resolution plan. Gabby emphasizes a user's accomplishments so as to build confidence and increase self-efficacy.
- **(e)** Longitudinal Multi-Factor Health Behavior Change. One of the Gabby's key features is its ability to remember and build upon previous interactions. ¹⁸ Simultaneous intervention on multiple health behaviors is effective for many combinations of behaviors. ¹⁹ Gabby was developed to focus on common

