- (b) Staff Training. The Boston based research staff will provide a 6 hour training during a required one week FMSTP monthly training contact sessions at Motebang Hospital via the Zoom network (Month 15). Topics will include: (1) Maternity Outcomes in Lesotho and Preconception Care; (2) What is Gabby and How Does it Work; (3) How to Introduce Patients to Gabby; (4) How to Conduct the Gabby Risk Assessment; (5) How to Assist Patients to Reduce Health Risks Using the "My Health To Do List"; (6) Tips and Challenges to Using Gabby on a mobile device; and (7) Data Collection/Reporting.
- (c) Recruitment. In month 14, the FMSTP registrars will recruit 20 women from each of the 10 district hospitals for a 200 of total participants. Inclusion criteria are: (1) female resident of Lesotho; (2) age18-28 years; (3) English speaking; (4) have access to an android smartphone with internet or Wi-Fi access (e.g., hospital, at home, school, local library); and (5) are not pregnant. Each district hospital site will have a separate administrative page on the Gabby server where women will be enrolled with a unique username and password.
- (d) Implementation Roll Out. In months 14-16 women will be asked to use Gabby for three months and to discuss the relevant content areas identified by the risk assessment. Gabby will track progress and cross off risks once resolved. We will encourage FMSTP registrars to meet with participating women twice during the time they are using the system to discuss the health risks triggered and interventions suggested by Gabby.
- **(e)** Learning Communities and Support. The Boston based teams will be available for telephone support during weekdays for any implementation issues that arise. Each month during implementation, the Boston team will organize a one hour "Learning Community" webinar using the Zoom web conferencing designed for registrars and interested staff at the district hospitals. The webinar will provide tips that we have learned and provide facilitated discussion among sites about what works and challenges faced.

Implementation and Effectiveness Outcomes (Objective 3). To be completed during months 22-24.

- (a) Principles Guiding Evaluation. The evaluation will begin from the time that we initiate engagement with the implementation partners and continue throughout implementation efforts. The evaluation is guided by the 6-step framework described by the CDC.³⁰

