- (d) Quantitative Data for Implementation Outcomes. Implementation outcomes will include Site Demographics and Characteristics collected through RedCap surveys that will allow our team to investigate the association between the demographics of sites and higher levels of implementation success among sites; Site-level Technical Assistance logs maintained by our research team in order to track commonly encountered technical issues, document the appearance of any system bugs, and estimate the time spent identifying and resolving problems; and Client usage data from the server interrogation records participant-level information, including number of logons for each client enrolled, minutes of system usage per logon, and all responses to dialogue or decisions within the system, including risks chosen to discuss.
- (e) Evaluation of Effectiveness Outcomes. The second portion of our evaluation focuses on assessing the clinical effectiveness of the Gabby mHealth program in Lesotho. Clinical effectiveness data include: (1) Using de-identified data derived from the Gabby server, we will identify Health Risks from the risk assessment that were triggered by all women when they first log-on to Gabby. The definitions of how risks are defined and what responses trigger each risk are defined in appendix B. The distribution of risks will be compared among district hospitals. The frequencies of risks triggered will be compared to other populations (e.g., Healthy Start participants, college students) who have completed the Gabby risk assessment in the past. Also using de-identified data derived from the Gabby server, we will collect the Baseline and Follow-up Stage of Change Data collected by Gabby as part of the system dialogue for each risk triggered by a women in the risk assessment. Follow-up stage of change data will allows us to track

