progress (or regression) in the changes associated with each health risk (e.g., folic acid use, minutes of daily exercise, number of cigarettes smoked per day). We will analyze of Stage of Change data by calculating the proportion of women who have (1) advanced to the maintenance stage, and (2) progressed from pre-contemplation, contemplation, preparation, and action to a higher stage, that could be one or more steps. The former represents the type of measures that have been typically employed as outcome measures for studies focusing on individual risk factors. The latter is more sensitive, but not been widely employed in previous research.

Disseminate the Results. (Objective 4). In months 23-24, we will disseminate our results to the information technology, health services, global health and public health research and policy communities through presentations at national and international conferences and interviews with journalists and consumer publications including those in low income countries, and academic publications in peer reviewed journals.

References

- StatsCounter Global Stats. Mobile Operating System Market Share Lesotho). http://gs.statcounter.com/osmarket-share/mobile/lesotho). Accessed August, 16, 2018.
- ³ Kreuter MW, Strecher VJ, Glassman B. One Size Does Not Fit All: The Case for Tailoring Print Materials. The Society of Behavioral Medicine 1999;21(4):276-283.
- Prochaska JO. Multiple Health Behavior Research Represents the Future of Preventive Medicine. Preventive Medicine 2008;46:281-285.

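### Stage of change is summarised only by upward moves and no comparator is described, so the planned figures cannot separate improvement from two-way movement

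*Combined protocol and SAP*

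**What the plan says.** All references are to the combined protocol and SAP.

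- **What is recorded.** Objective 3, item (e), Evaluation of Effectiveness Outcomes, takes baseline and follow-up stage from the server, "collected by Gabby as part of the system dialogue for each risk triggered by a women in the risk assessment". The follow-up data are said to allow tracking of "progress (or regression) in the changes associated with each health risk". Which answers trigger a risk is left to an appendix: "what responses trigger each risk are defined in appendix B".
- **What is analysed.** The next sentence gives the whole stated analysis: "calculating the proportion of women who have (1) advanced to the maintenance stage, and (2) progressed from pre-contemplation", contemplation, preparation or action to any higher stage, by one step or more. The first measure is described as typical of "outcome measures for studies focusing on individual risk factors".
- **Who is studied.** Objective 2, item (c), Recruitment, has the registrars "recruit 20 women from each of the 10 district hospitals". All are asked to use the system. Objective 3(e) compares hospitals, and compares this population with others, on the risks triggered and not on stage movement.
- **What the figure is for.** Purpose/Study Objective names stage of change, content knowledge and system usage as the bases for judging effectiveness. The Hypothesis is about progression through the stages. The Goal paragraph makes effectiveness the secondary focus, after implementation and dissemination.

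**The concern.** A share that counts only upward moves is above zero whenever anyone moves up. With a control group, the control arm would show how much of that share is ordinary movement. Here none is described, so the downward share is the only check available within the data, and it is not among the planned figures.

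At stake is how the result will be read. Gabby Has Proven Efficacy in RCTs reports that 67% of women who began as contemplative were later in action or maintenance, and takes this as a sign of success. That is an upward share without a comparator. (The same paragraph also reports that most pre-contemplative women took no further action.) The planned figures invite the same reading, and the results are to be published under Objective 4.

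**Working it through.** **1. Inputs.** From the documents: five stages (Motivational Interviewing, item d) and 20 × 10 = 200 women (Recruitment), which reproduces the stated total. No expected progression rate, test, alpha or power is given, so there is no planned stage figure to reproduce. All movement rates below are assumptions for illustration.

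**2. The logical point, which needs no assumed rate.** Among women with both stages for a given risk, let U, S and D be the shares that moved up, stayed and moved down, with U + S + D = 1. Planned measure (2) uses U. Net change is U − D. D does not enter the planned measure, so the same figure fits different results:

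- U = 20%, D = 0%: planned figure 20%, net 20 − 0 = +20 points.
- U = 20%, D = 20%: planned figure 20%, net 20 − 20 = 0.

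**3. The same point in counts** (one risk per woman, n = 200, assumed counts):

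| Up | Down | Planned figure | Up minus down |
|---|---|---|---|
| 60 | 0 | 60/200 = 30% | +30 points |
| 60 | 20 | 30% | 40/200 = +20 points |
| 60 | 60 | 30% | 0 |
| 60 | 80 | 30% | −20/200 = −10 points |

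**4. Measure (1) has the same fault.** Assume 40 women in each of the five stages, with a 20% chance of moving one stage up and 20% of moving one stage down wherever that move exists.

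- Up: 4 stages × 40 × 0.20 = 32 women. Down: 4 × 40 × 0.20 = 32 women. The stage distribution at follow-up is unchanged.
- Measure (2): 32/160 = 20% of women below maintenance, or 32/200 = 16% of all women.
- Measure (1): 40 × 0.20 = 8 women newly reach maintenance. Another 40 × 0.20 = 8 leave it, and they are not counted.

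**5. Limit of net change.** In the same example, suppose behaviours already at maintenance do not trigger a risk, so those 40 women are never staged. Up is still 32. Down loses the 8 who left maintenance: 32 − 8 = 24. Net is (32 − 24)/160 = +5 points, with no true change in the population. Including every baseline stage in the denominator cannot correct this if the maintenance group was never entered. The answer lies in Appendix B.

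**6. Women with several risks.** Stage is recorded per risk but the proportions are of women. If risks were combined by counting any upward move, then with an assumed 5 independent risks, each 10% up and 10% down, 1 − 0.9^5 = 41.0% of women would count as progressed, and the same 41.0% as regressed. Under any such rule the upward share needs its downward counterpart.

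**The case against.** **Regression is already in the plan.** The sentence just before the analysis gives tracking of regression as a use of the data. This stands in part: a reader might infer that downward moves are not recorded, and that would be wrong. But the analysis sentence does not use them. The gap is in the summary, not in data collection.

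**Little rests on the figure.** Effectiveness is secondary, stage of change is one of three bases for judging it, and no test or threshold is attached. This stands, and it keeps the point at the level of a cheap improvement.

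**The remedy is imperfect.** Step 5 shows that net change can also exceed zero with no true change, and Appendix B was not available to settle whether it would. This stands. Net change also does not attribute movement to the app: if women improve for other reasons and none regress, it still credits the whole gain.

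**Stronger readings that the documents do not support.**

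- A reader might take the 20.5% (224/1,091) of risks resolved among women sent only a letter, in the earlier 100-woman trial, as the upward movement to expect here without the app. It is a different outcome, in a trial with a six-month intervention period, and it bears on the missing comparator and not on downward moves.
- A reader might infer that the woman-level figure will be inflated by counting any risk. The reference to individual risk factors suggests one proportion per risk, and neither a combining rule nor the number of risks per woman is given.
- A reader might infer that the upward share will overstate benefit by some known amount. No downward rate or misreporting rate is given, so no such amount can be stated.

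**Conclusion.** The point holds as a limited one. The two planned summaries count upward moves only and no comparator for stage movement is described, so a positive figure does not by itself show improvement. The size that can be stated without assumed rates is the ambiguity itself: one planned value of 20% is compatible with a net change of +20 points or of 0. The 200-woman counts, the 20% movement chance and the five-risk example only illustrate it.

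This does not show that the app is ineffective, that downward movement will be common, or that net change would be an unbiased effect. It is worth correcting because stage progression is the subject of the hypothesis and the needed data are already to be collected.

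**What to change.** In Objective 3(e), keep the two planned proportions and add:

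- for each risk with a baseline and a follow-up stage, the baseline-by-follow-up stage table, with percent up, same and down, and up minus down beside them, all baseline stages included;
- the number of triggered risks with no follow-up stage, which matters because "Discussion is directed by the woman based upon her interests and motivations" (Tailored Health Content);
- if a woman-level proportion combining several risks is reported, the rule used and the proportion who regressed under that same rule;
- a statement that the result is an uncontrolled before-after change;
- a statement, taken from Appendix B, of whether maintenance-stage behaviours trigger a risk. If they do not, say that up minus down can be above zero with no true change and is descriptive only.

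The cost is analysis wording and a little more tabulation. No new data, visits or participants are needed. The downside for the sponsor is that the upward share, itself unchanged, will be read beside a downward share that may make it look less favourable.
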